### 12.1 End of Study

The end of study will occur when all patients have been followed for 1 year or death, withdrawal of consent, or are lost to follow-up.

## 13.0 CRITERIA FOR OUTCOME ASSESSMENT AND ENDPOINT EVALUABILITY

### 13.1 Criteria for Therapeutic Response/Outcome Assessment

To assess subjects in the Benralizumab achieving treatment success, defined as grade  $\leq 1$  rash rate at 4 weeks, as assessed by the NCI CTCAE v5.0.

*Quality of Life:* QOL will be assessed by the Functional Assessment of Cancer Therapy–Breast (FACT-B) (version 4) scale Appendix 3. The FACT-B contains 37-items, divided into four primary subscales for physical well-being (7 items), functional well-being (7 items), emotional well-being (6 items), and social/family well-being (7 items) that comprise the FACT–General (FACT-G) scale, in addition to a breast cancer subscale (10 items). The five subscales will be summed to obtain the FACT-B score (for a total score of 148). We will also compute the FACT-G score (27 items, excluding the breast cancer subscale; total score of 108). All items are rated on a 0 to 4 Likert scale, using the following response format: 0 = not at all; 1 = a little bit; 2 = somewhat; 3 = quite a bit; 4 = very much. Respondents are asked to respond to each question as it applies to the past 7 days. Higher scores on the FACT-B indicate higher QOL. Internal consistency for the FACT-G and FACT-B is well established. The PRO-CTCAE for rash, and other alpelisib AEs (i.e mucositis, diarrhea) will be administered at every visit.

### 13.3 Exploratory Endpoints

1. Explore the change in serum and skin inflammatory markers from baseline to 4 weeks (using non-invasive skin tape for skin).
2. Explore the change in histologic markers from skin biopsies in patients with rash, including eosinophil counts, CD4/8 count, IL-5, PI3 kinase pathway activation; at rash onset and at 28 days.

***Skin tape strips (STS) sample acquisition.*** In this study STS will be collected from each study

Memorial Sloan Kettering Cancer Center  
[name]  
[name]

participant at the initiation of treatment, day 14 and day 28 of the study. At each time point twenty large D-Squame tape strips (CuDerm; Ø30mm) will be collected from the designated skin area with no lesions. If on day 14 or day 28 skin rash is present, STS sampling of the lesional area will be performed as well. D-Squame D500 pressure instrument will be used to apply equivalent pressure (225 g/cm^2) for STS collection. Collected STS will be stored adhered to storage cards (CuDerm) to minimize air exposure of the collected material and kept frozen at - 80°C prior to processing.

**Protein extraction from STS.** Due to the relatively small quantity of biomaterial collected from the skin with adhesive STS, our protocol was optimized to minimize the total volume of extraction buffer for each sample. Extraction chambers containing individual STS (in extraction buffer) will be placed in a Cole-Parmer 8891 bath sonicator for 30 minutes at 40kHz at 65W. After the sonication, STS will be removed from the buffer, protein extracts will be transferred into microtubes and centrifuged to clear cell debris and tape adhesive residue. Samples will be cryopreserved for future analysis. Total protein levels in STS extracts will be measured with NanoOrange Protein Quantitation Kit (Invitrogen).

**MSD multiplex assay from plasma.** Protein extracts will be analyzed using the MSD U-Plex human cytokine multiplex platform. We will aim to profile the expression of cytokines and chemokines in the skin prior and during rash development targeting Th1, Th2, Th17 and general inflammation (general inflammation: IL-1a, IL-1b, IL-18, IL-6, and IL-8; Th2 cytokines: CCL17, CCL22, TSLP, IL-33, IL-13, IL-4, IL-5, IL-22, IL-31, and eotaxin 3; Th1/Th17 cytokines: IL-12, IL-17a, IL-17c, IL-IL-23, and IP-10). For statistical analysis, cytokine concentrations below the fit curve range (signal below the bottom of the bottom-of-the-curve fit, no concentration given) will be assigned the value of the lowest sample concentration detected below the standard curve detection limit to maintain the ranking order. The MSD assay results will be normalized to the total protein in each sample.

**Assessment of skin biopsies.** Skin biopsies will be collected from the skin site with rash. Skin biopsy will be fixed in 10% buffered formalin. Preserved skin biopsies will be paraffin embedded and sectioned. Skin biopsy sections will be used to assess inflammatory cell infiltrates and inflammatory mediators in the skin through RNA transcripts profiling and immunostaining.

**RNA preparation and real-time RT-PCR.** RNA FFPE kit (Qiagen) will be used for RNA extraction from FFPE preserved skin biopsy samples according to the manufacturer's protocol. RNA will be reverse-transcribed into cDNA using SuperScript VILO MasterMix (Life Technologies, Thermo Fisher Scientific). cDNA will be analyzed by real-time RT-PCR using an ABI Prism 7300 sequence detector (Applied Biosystems, Thermo Fisher Scientific). Primers and probes for selected gene targets will be purchased from Applied Biosystems, Thermo Fisher Scientific.

**Immunofluorescence staining.** Skin biopsy sections will be stained with the specific antibodies to detect tissue eosinophils, lymphocytes, IL-5 and PI3 kinase pathway activation. Visualization of additional inflammatory cytokines/chemokines of interest will be considered based on the results of the inflammatory mediator assessment from the multiplex MSD assays of protein extracts prepared from STS samples. Nuclei will be visualized with DAPI, and wheat germ agglutinin-conjugated FITC will be used to stain the cytoskeleton. The slides will be visualized with fluorescence microscopy (Leica) Slidebook 6.0 (Intelligent Imaging Innovations) will be used for data analysis. Skin biopsy sections from healthy control subjects obtained through other studies will be used for comparison.

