the Benralizumab group over the study period will be compared using the Wilcoxon Rank Sum test. Time to the development of grade 1 or 2 rash will be evaluated using Kaplan-Meier time to event curves and assessed using the log rank test and Cox proportional hazards regression analysis. The Yates corrected chi square test will be used to compare the frequency of non-skin alpelisib related adverse events between groups, as well as 6 and 12 month ORR and PFS. Differences between the Benralizumab group on IL-5 inhibition and antihistamines and non-skin alpelisib related adverse events will be evaluated using linear mixed models. Changes in inflammatory biomarkers in skin and related to rash and all other exploratory endpoints will only be evaluated graphically with descriptive statistics. Given the exploratory nature of the current trial, there will be no adjustments for multiplicity. All the statistical analyses will be performed using SAS® Version 9.4 or higher. De-identified data will be shared via MSK secured e-mail quarterly to Augmentium Pharma Consulting for statistical analysis.

Patients may be removed from the study for various reasons as outlined in section 12.0 of the protocol. Descriptive statistics will be reported separately for patients removed from the study, including a summary of reasons for removal, their median duration in the study and range, median, range, and the distribution of rash grades at all follow-up times prior to their removal from the study.

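### Undetectable tape-strip cytokines receive one constant that is then apparently divided by each sample's total protein, so a cytokine undetectable at both visits shows a change that is only the inverse change in protein yield

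*Combined protocol and SAP*

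**What the plan says.** All of this is in section 13.3 (Exploratory Endpoints) unless noted.

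- **Which values are replaced.** The multiplex assay paragraph covers readings described as "signal below the bottom of the bottom-of-the-curve fit, no concentration given".
- **What replaces them.** Such a reading "will be assigned the value of the lowest sample concentration detected below the standard curve detection limit to maintain the ranking order". This is one constant, on the concentration scale.
- **What follows.** The next sentence is "The MSD assay results will be normalized to the total protein in each sample". It makes no exception for substituted values.
- **The denominator.** The protein extraction paragraph has total protein measured in the tape-strip extracts. That paragraph opens "Due to the relatively small quantity of biomaterial collected from the skin with adhesive STS".
- **What is sampled.** A designated non-lesional area is stripped at treatment start, day 14 and day 28. If rash is present on day 14 or 28, "STS sampling of the lesional area will be performed as well".
- **How results are used.** Exploratory objective 1 is the change in serum and skin inflammatory markers from baseline to 4 weeks. Section 14.0 (General Statistical Plan) says of the skin biomarkers and the rest that "all other exploratory endpoints will only be evaluated graphically with descriptive statistics". The immunofluorescence paragraph of section 13.3 adds that further staining targets may be chosen from the tape-strip assay results.

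The plan does not flag substituted values after normalization. It does not report the share undetectable or show protein yield by visit or lesion status.

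**The concern.** A placeholder shared by all undetectable samples keeps them tied at the bottom only while they stay on the scale on which it was assigned. Once each is divided by its own protein, the ties break and the new order among them is the inverse order of protein yield. Some may also move above samples in which the cytokine was measured.

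The within-patient change is more seriously affected. If a cytokine is undetectable at baseline and at day 28, the honest statement is that no change could be measured. The rule would plot a rise or fall instead, and nothing on the plot would show that it came from the amount of protein on the strips.

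The trial has a single arm with no concurrent control, so a systematic shift in yield over time cannot be removed by comparison. If rash skin yields a different amount of protein (an assumption), the same artefact could look like a rash effect. Section 13.3 also intends to compare skin before and after rash onset. A spurious pattern could influence which additional mediators are stained in the biopsies.

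**Working it through.** The plan states no figure here, so there is none to reproduce. The first two results are algebra; the rest is illustration.

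**Notation.** c = the assigned constant; P = a sample's total protein; c_det = a measured concentration. A substituted value becomes c/P.

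**1. Undetectable at both visits.** Fold change = (c/P1)/(c/P0) = P0/P1. The constant cancels. If yield at day 28 is 70% of baseline, the plot shows a 1/0.70 = 1.43-fold rise. If it is 50%, the plot shows a 2.0-fold rise.

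**2. Rank order.** An undetectable sample outranks a detected one when c/P_nd > c_det/P_det, that is, when P_det/P_nd > c_det/c. With equal protein in all samples this never happens and the fold change in step 1 is 1.0. The problem therefore depends on protein varying.

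**3. Hypothetical example.** Assigned value 0.05 pg/mL.

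| Sample | Concentration (pg/mL) | Protein (mg/mL) | Normalized (pg/mg) |
|---|---|---|---|
| Undetectable A | 0.05 (assigned) | 0.010 | 5.0 |
| Undetectable B | 0.05 (assigned) | 0.040 | 1.25 |
| Detected C | 0.10 | 0.040 | 2.5 |

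A and B differ 4-fold because of protein alone. A ranks above C because the protein ratio, 0.040/0.010 = 4, exceeds the concentration ratio, 0.10/0.05 = 2. B stays below C because its protein ratio is 1. In truth A is only known to lie below its own limit per mg, so the data do not order A and C.

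**4. How often an apparent 2-fold change arises.** Assumptions, none from the documents: analyte per mg log-normal with log-SD 1; protein log-normal with log-SD 0.3, 0.5 or 0.8; concentration = analyte per mg × protein; 50% of samples undetectable; assigned value 0.8 × the limit; visits independent.

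Across all pairs, the share with P0/P1 at least 2-fold in either direction is 2 × [1 − Φ(ln 2 / (s√2))], where s is the protein log-SD. That gives 10%, 33% and 54%. These are not the right figures for pairs undetectable at both visits. Low-protein samples are more likely to be undetectable, so conditioning narrows the protein spread. Simulation with that conditioning gives:

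| Protein log-SD | All pairs | Undetectable at both visits |
|---|---|---|
| 0.3 | 10% | 9% |
| 0.5 | 33% | 29% |
| 0.8 | 54% | 48% |

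If each patient's per-mg level is held stable between visits, the conditioned figures fall slightly, to 8%, 25% and just over 42%.

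**5. Rank order in the same model.** An undetectable sample lands above a detected one in about 8%, 18% and 34% of such pairs. Of those pairs, 27% at log-SD 0.3 and 32% at 0.5, rising to just over a third at 0.8, are nonetheless in the true per-mg order. Over all undetectable-versus-detected pairs, dividing the placeholder agrees with the true order in 94%, 87% and 78%. Leaving undetectable samples tied at the bottom agrees in 97%, 94% and 87%.

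**The case against.** **The order of steps is inferred.** The two sentences are adjacent, but the plan never says that one operation follows the other, and the substitution is introduced as preparation for statistical analysis. This stands as a caveat. Substitution before division remains the natural reading: the constant is a sample concentration, and inserting it among normalized values would mix units. If another order is meant, the text still needs to say so.

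**Collection is standardized.** Section 13.3 fixes twenty strips, a set pressure and a designated non-lesional area, and lesional strips are additional. This should reduce variation in yield, but it does not guarantee equal protein. Normalizing to protein only makes sense if protein is expected to differ.

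**Nothing confirmatory depends on it.** This stands in full. Section 14.0 limits these endpoints to graphs and descriptive summaries.

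A reader might infer four stronger things that the documents do not support:

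- *That rank order always fails.* It fails only when the protein ratio exceeds the detected-to-assigned concentration ratio.
- *That the 8% to 34% in step 5 is an error rate.* A sizeable minority of those pairs are in the true order, and under sample-specific censoring some have no determinable order.
- *That particular targets such as IL-5, IL-4 or IL-13 will mostly be undetectable.* The documents give no detection rates. They only provide a rule for undetectable values.
- *That blood cytokines would be divided by a protein value that is never measured.* The paragraph heading mentions plasma, but its text concerns protein extracts and skin, and the staining paragraph refers to the assays as run on tape-strip extracts. This is a heading slip.

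Dividing detected values by protein is ordinary practice and is not criticized here.

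**Conclusion.** The point holds, at minor severity. Read naturally, the rule does not guarantee the ranking it sets out to keep. For a cytokine undetectable at both visits it reports the inverse change in protein yield as a cytokine change. Given that order of steps, this second result is exact and needs no numerical assumption.

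Its practical size cannot be determined from the documents. The 9% to 48% of both-undetectable pairs with an apparent change of 2-fold or more rests entirely on the assumed protein variability, undetectable share and independent visits set out above. If protein were nearly equal across samples, the effect would be negligible.

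The consequence is limited to the descriptive skin-marker plots under exploratory objective 1 and to the choice of additional staining targets. The primary endpoint, sample size and safety analyses are untouched.

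**What to change.** Amend the multiplex assay paragraph of section 13.3 as follows:

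1. Normalize detected values only.
2. Treat undetectable values as left-censored at the sample-specific limit (assay limit divided by that sample's total protein), and mark them with a distinct symbol in plots.
3. Report percent detectable and total protein by visit and by lesion status beside each cytokine.
4. Summarize fold change only for cytokines detectable in most samples, with the cut-off stated in advance.

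Simply tying undetectable values at the lowest rank after normalization would serve the stated ranking aim. It would still impose an order on pairs that the data do not order, so censoring is preferable.

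The cost is a few sentences of analysis wording, with no new sample or assay. The small downside is that poorly detected cytokines are reported as percent detectable rather than as a fold change.

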### Novelty of proposed studies

Proposed exploratory studies will provide novel insights about the longitudinal production of inflammatory mediators and cytokines in the multiplex format in the skin of cancer patients with

targeted PI3 kinase inhibition with alpelisib and concomitant inhibition of IL-5 or histamine signaling during the course of therapy. The information about the production of these mediators in patients that do not develop skin rash, or in the skin with skin rash before and after skin rash onset will be acquired.

The study will allow visualization of inflammatory infiltrates and IL-5 production in skin biopsies from patients with rash despite treatment with anti-IL5 receptor blocking antibody or histamine H1 inhibitor, to determine what type of skin inflammatory response persists in patients with skin rash and whether skin tissue eosinophil and IL-5 elimination was efficient.

The study will explore evidence of PI3 kinase pathway inhibition in skin biopsies from cancer patients with rash.

## 14.0 BIOSTATISTICS

### Sample Size

This will be a single arm trial. The target sample size is intended to test the hypothesis that benralizumab reduces the frequency of grade  $\geq$  grade 2 rash at 4 weeks relative to the historical controls in patients receiving alpelisib. The primary endpoint in the current study will be the proportion of patients to achieve a rash grade of 1 or less. It has been reported that approximately 34% of patients receiving alpelisib will develop  $\geq$  grade 2 rash within the first 30 days. An increase in rash control to approximately 88% is deemed to be clinically meaningful with the investigational agent. Sample sizes of 57 patients achieves an 80% power to detect a difference based on a two sample proportions test. Due to potential attrition during the course of the study, the sample size will be increased by 10%. The resultant sample size will be 63 patients.

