## 1.0 PROTOCOL SUMMARY AND/OR SCHEMA

This is a multi-center, open-label, phase 2 trial testing the efficacy and safety of 2 interventions that target rash during PI3K inhibitor therapy in postmenopausal women and men with histologically-confirmed, hormone receptor (HR)-positive, HER2-negative, PIK3CA mutant metastatic breast cancer (MBC). A total of 63 patients will be enrolled into one arm: benralizumab 30mg in combination with standard of care (SOC) endocrine therapy (fulvestrant or AIs or aromatase inhibitors (AIs)) and PI3K inhibition (alpelisib). A total of 43 patients will be enrolled at MSKCC and a total of 20 patients will be enrolled at the participating external institutions (10 patients at Stanford University and 10 patients at Dana Farber Cancer Institute). The primary endpoint is the proportion of patients with grade  $\leq 1$  rash rate at 4 weeks.

**Patient Population:** The primary study population will be postmenopausal women and men with histologically-confirmed, HR-positive, HER2-negative, *PIK3CA* mutant MBC who have received no more than 2 lines of endocrine-based therapy in the metastatic setting.

**Design:** A multi-center, open-label, phase 2 trial testing the efficacy and safety of one interventions (one anti IL-5 receptor antibody and one antihistamine) that target the maculopapular rash during PI3K inhibitor therapy in patients with HR-positive, HER2-negative, *PIK3CA* mutant MBC receiving first or second line therapy. Study participants (n=112) will enrolled to one arm: benralizumab (anti-IL5ra) in combination with SOC endocrine therapy (fulvestrant or AIs) and PI3K inhibition (alpelisib). The primary endpoint is the grade  $\leq 1$  rash rate at 4 weeks. The study size is determined to compare the grade  $\leq 1$  rash rate at four weeks with historical controls. It has been reported that approximately 34% of patients receiving alpelisib will develop  $\geq$  grade 2 rash within the first 30 days. The corollary is that 66% of historical controls will have grade  $\leq 1$  rash within the first 30 days. An increase in rash control to approximately 88% is deemed to be clinically meaningful with the investigational agent under investigation (IL5r antibody). A sample size of 57 patients per group will achieve an 80% power to detect an odds ratio of 4.0 with respect to the primary endpoint. The proportion in the experimental group is assumed to be 0.66 under the null

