hypothesis and 0.88 under the alternative hypothesis. The proportion is 0.66. If it is assumed that 10% of patients will withdraw consent or be lost to follow up, then 63 patients will need to be enrolled into this trial.

**Treatment Plan:** All participants will receive SOC endocrine therapy (fulvestrant or AIs) and PI3K inhibition (alpelisib). Participants will receive benralizumab 30mg subcutaneously on day -1. All participants will be monitored at regular visits for the duration of the trial. After 4 weeks, patients will be followed for safety at 90 days and disease progression for 1 year.

**Estimated Time to Completion:** 1 years.

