### 3.3 Alpelisib for the Treatment of HR-positive MBC

Alpelisib is an oral,  $\alpha$ -specific PI3K inhibitor that has been recently approved in combination with fulvestrant for the treatment of postmenopausal women, and men, with  $HR^+$ ,  $HER2^-$ ,  $PIK3CA$ -mutated, MBC following progression on or after an endocrine-based regimen. In the phase 3 SOLAR-1 trial, an improvement in progression-free survival (PFS) was observed in  $PIK3CA$ -mutated patients treated with alpelisib plus fulvestrant (n=169) compared with placebo plus fulvestrant (n=172) (11 mo vs 5.7 mo; hazard ratio [HR] 0.65,  $P<0.001$ ). Overall response rate (ORR) and clinical benefit rate (CBR) in the  $PIK3CA$ -mutated cohort were greater in the alpelisib-fulvestrant or Als group compared with the placebo-fulvestrant or group (ORR 26.6% vs 12.8%; CBR 61.5% vs 45.3%). The most common AEs reported in the safety population for alpelisib (n=284) and placebo groups (n=287) were hyperglycemia (63.7% vs 9.8%), diarrhea (57.7% vs 15.7%), nausea (44.7% vs 22.3%), decreased appetite (35.6% vs 10.5%), rash (35.6% vs 5.9%), or maculopapular rash (14.1% vs 1.7%). Serious AEs (SAEs) were reported by 99 (34.9%) alpelisib-treated patients and 48 (16.7%) placebo-treated patients. Permanent discontinuation due to AEs occurred in 71 alpelisib-treated patients (25%) and 12 (4.2%) placebo-treated patients. The most common AEs leading to discontinuation of alpelisib were hyperglycemia (18 patients, 6.3%) and rash (9 patients, 3.2%). The combination of fulvestrant or Als and alpelisib is now a new standard of care therapy in the treatment of  $ER^+$   $PIK3CA$ -mutant MBC.

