### 3.4. Dermatologic adverse events to PI3K inhibition with alpelisib

Second to hyperglycemia, rash has been reported as a common cause of discontinuation of alpelisib (3.2%), signifying an obstacle to achieving therapeutic benefit. Maculopapular rashes related to alpelisib are likely an on- target effect of PI3K inhibition, occurring in 57% of patients. While alpelisib has high selectivity to inhibit the p110 $\alpha$  subunit of PI3K $\alpha$ , small molecule inhibitors with selectivity against various combinations of PI3K isoforms, such as buparlisib, have also demonstrated frequent dAEs with similar maculopapular morphology. Our most extensive in-human experience is with the pan-PI3K inhibitor buparlisib (BKM120, Novartis). Despite the neurologic adverse events that preempted FDA-approval, trials with buparlisib illustrated many safety issues and was a preview for adverse events of other candidate inhibitors of the PI3K pathway. In a phase I study for buparlisib, a primarily pruritic maculopapular rash concentrated on the torso was observed. For grade 3/4 rash occurring in two or more patients, the incidence was 11%; and for all-grade rash, the incidence was 43%. In the BELLE-2 phase III study, there was a 32% incidence of rash, with 8% grade 3/4 rash. Experience with idelalisib, copanlisib, and duvelisib continues to report significant dAEs. Idelalisib, a PI3K $\delta$  specific inhibitor, reported a 13% incidence of any grade rash, with 2–3.6% incidence of grade 3 rash. With copanlisib, which selectively inhibits PI3K $\alpha/\delta$ , maculopapular rash of any grade was noted in 13–16% of all patients with grade

3 rashes occurring in 7–13% of patients. In patients receiving duvelisib, which targets p110 $\gamma/\delta$ , maculopapular rash was observed in 16.2–18.6% of patients, and grade 3 rash was seen in < 5% of patients. It is unlikely that the diverse chemical structures represented in these PI3K inhibitors have similar non-specific activities that cause maculopapular rash.

[figure not shown]

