Previous analyses suggests that histamine producing cells and eosinophils have some role in alpelisib-related rash. All patients receiving alpelisib have a trend towards increased eosinophils, with a more pronounced effect in patients with rash. Interestingly, pre-treatment absolute eosinophil count may be lower in patients who develop rash. We also found that patients developing rash had a statistically significant increase in eosinophils after 2 weeks of

receiving alpelisib ( $p < 0.05$ ) (below, left). This has also been demonstrated in phase 1

study of alpelisib in combination with fulvestrant or Als (below, right). Prospective analyses and anecdotal experience at MSK with over 100 patients has revealed that 90% of rash develops within the first 4 weeks. Indeed, the median time to onset of grade 3-4 rash was 13 days in the pivotal SOLAR-1 trial.

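### The sole comparator for the primary claim, 34% grade 2+ rash (null 0.66), has no stated source or precision and is not reconciled with the protocol's other alpelisib rash figures

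*Combined protocol and SAP*

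**What the plan says.** Section 14.0 (Sample Size) states "It has been reported that approximately 34% of patients receiving alpelisib will develop" grade 2 or worse rash in the first 30 days. Section 1.0 adds "The corollary is that 66% of historical controls will have grade" 1 or less, and sets the hypotheses: "The proportion in the experimental group is assumed to be 0.66 under the null" "hypothesis and 0.88 under the alternative hypothesis". Neither place names a cohort, a number of patients, the rash terms counted or a confidence interval.

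The background gives three other alpelisib rash figures. Section 3.3 reports "rash (35.6% vs 5.9%), or maculopapular rash (14.1% vs 1.7"%) for alpelisib versus placebo in the pivotal trial (284 alpelisib patients), without grades. Section 3.4 puts maculopapular rash at "occurring in 57% of patients", also without grades, and says that at the lead centre "90% of rash develops within the first 4 weeks".

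On the test, section 14.0 says "Sample sizes of 57 patients achieves an 80% power to detect a difference based on a two sample proportions test", and section 1.0 describes the 57 as a per-group number. The General Statistical Plan then proposes a logit model with a group-by-time term. No control data set, success cutoff, alpha or sensitivity analysis on the benchmark is specified.

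**The concern.** In a single-arm trial the benchmark does the work of a control group. If untreated alpelisib patients keep rash at grade 1 or less more often than 66% of the time, the trial will credit benralizumab with control they would have had anyway. If they do so less often, the trial understates the drug. Nothing inside the trial can reveal either error.

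Three features make the number hard to rely on.
- It cannot be traced or given a standard error.
- It is not squared with the protocol's other rash figures, one of which leaves no room for it.
- It counts any grade 2+ rash over 30 days, while sections 1.0 and 13.1 word the endpoint as the grade at 4 weeks, with a visit window of 7 days either side in section 11.0. A rash that has settled by that visit counts in the benchmark but might not count in the trial.

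**Working it through.** **Inputs.** Benchmark 34%, null 0.66, alternative 0.88, n=57 and 80% power (sections 1.0 and 14.0). Rash 35.6% and maculopapular rash 14.1% (3.3). Maculopapular rash 57%, and 90% of rash by week 4 (3.4). Alpha is not stated; two-sided 0.05 is assumed because it reproduces the plan's 57.

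**1. The plan's sample size.** Two-sample formula, pooled variance under the null:

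n = [1.96√(2×0.77×0.23) + 0.842√(0.66×0.34 + 0.88×0.12)]² / 0.22² = 56.2, so 57 per group.

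Treating 0.66 as fixed:

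n = [1.96√(0.66×0.34) + 0.842√(0.88×0.12)]² / 0.22² = 29.8, so 30.

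The 57 therefore allows for sampling error in a control group of 57. That group is not identified anywhere.

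**2. Does 34% fit the other figures?**

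| Any-grade rash | By week 4 (×0.9) | Share that must be grade 2+ |
|---|---|---|
| 35.6% | 32.0% | 34/32.0 = 106%: impossible |
| 35.6% + 14.1% = 49.7% (no overlap) | 44.7% | 34/44.7 = 76% |
| 57% | 51.3% | 34/51.3 = 66% |

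The text gives no grade split for alpelisib rash, so the 66% and 76% cannot be checked. They also show that the error has no fixed direction. On the 57% figure, a 60% share gives a control success rate of 1 − 0.513×0.6 = 0.69, above the null. A 70% share gives 1 − 0.513×0.7 = 0.64, below it.

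**3. What an error in 0.66 does.** The plan states no cutoff, so take an exact one-sided 2.5% test of 0.66 at n=57. It succeeds at 45/57 (78.9%) or more, with 98.4% power at 0.88. The chance of success with no drug effect is P(X ≥ 45), X ~ Binomial(57, p):

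| True control rate p | 0.62 | 0.66 | 0.70 | 0.75 |
|---|---|---|---|---|
| Success with no drug effect | 0.5% | 2.4% | 8.9% | 30% |

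**4. Sampling error in the 34%.** The denominator is unknown, so these are assumed. Exact 95% intervals: 17/50 gives 21–49%, 34/100 gives 25–44%, 97/284 gives 29–40%. Averaging the step 3 probability over a beta distribution for the control rate gives about 8%, 5% and 3.5% respectively, against 2.4% with 0.66 fixed.

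**5. Time frame.** Suppose the endpoint means status at the visit, and a share f of grade 2+ rashes has fallen to grade 1 or less by then (assumed). The untreated rate is 1 − 0.34(1 − f). For f = 10%, 20% and 40% this is 0.69, 0.73 and 0.80, and step 3 gives 7%, 19% and 62%. This component can only raise the control rate.

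**6. The bar against a real cohort.** Assume 66/100 controls and a pooled two-sided z test at 0.05.
- 46/57: difference 0.147, standard error √(0.713×0.287×(1/57+1/100)) = 0.0750, z = 1.959. This just misses 1.960.
- 47/57: difference 0.165, standard error 0.0745, z = 2.21. This passes.

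The bar moves from 45 to 47. Power for 0.88 against 0.66 with 57 and 100 patients: pooled rate (57×0.88 + 100×0.66)/157 = 0.740, null standard error 0.0728, alternative standard error √(0.1056/57 + 0.2244/100) = 0.0640, and (0.22 − 1.96×0.0728)/0.0640 = 1.21, so about 89%.

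**The case against.** A reader might infer that 34% contradicts the protocol's own rash data. The documents do not support that. It fails only against 35.6% taken alone, leaving out the maculopapular term listed beside it, although maculopapular rash is what the trial targets. Even that conflict mixes cohorts: the 90% is the lead centre's experience and the 35.6% is from the pivotal trial. The grade 2 definition in Table 2 is broad, so a 66% to 76% share is not implausible. Figures in section 3.4 could not be read and may bear on it. What stands is that the text does not reconcile the numbers.

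A reader might also infer that the trial is likely to succeed without a drug effect. That needs a true control rate above 0.66, which the documents neither show nor rule out. Below 0.66 the test is conservative. A scenario in which only half of rashes are grade 2+ has no basis in the documents and shows one direction only.

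Nor is 0.66 treated as exactly known throughout. Section 1.0 states it as the null, but the 57 is a two-sample size and the planned model has a group term. The 45/57 rule is an illustration and not the plan's rule. This objection moves the defect without removing it: the sizing and the model presume a control group that is never identified.

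On the time frame, the primary objective speaks of incidence, and the evaluability sentence in section 12.0 refers to a rash event before 4 weeks. Both lean towards a cumulative endpoint, in which case the mismatch largely disappears. The plan still has to say which is meant.

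Finally, this is a phase 2 trial that calls itself exploratory and will report 95% intervals, so readers can set the lower limit against any benchmark. That lowers the severity. It does not supply a comparator.

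**Conclusion.** The point holds in this form: the only comparator for the primary claim is undocumented, carries no precision, is not reconciled with the protocol's other alpelisib figures, and may be on a different time basis from the endpoint. The likely direction of error cannot be determined. Under the illustrative rule, a benchmark that is right gives 2.4% false success. One that is 4 points too low gives 8.9%, 9 points too low gives 30%, and 4 points too high gives 0.5%. If the 34% came from about 100 patients, sampling error alone takes the average to about 5%.

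These sizes rest on an assumed alpha, cutoff and denominator, because the plan gives none. The reproduction of 57 as a two-sample number and the 32.0% against 34% conflict use only the documents' figures, apart from the assumed alpha and the transfer of the 90% to the pivotal trial. This should be fixed before any efficacy analysis; it is not a reason to call the design invalid.

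**What to change.** In sections 1.0 and 14.0, before any efficacy analysis:

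1. Identify the historical cohort, for example the experience of over 100 patients in section 3.4. Give its denominator and its grade 2+ rash count, using the same rash terms and time frame as the trial endpoint. State whether that endpoint is cumulative to 4 weeks or status at the 4-week visit, and explain how the result relates to 35.6%, 14.1% and 57%.
2. Base the primary comparison on that count and denominator with a two-sample test, as the sample size already assumes, instead of a fixed 0.66. State alpha and sidedness.
3. Report the lower 95% limit of the benralizumab success rate explicitly as the highest control rate the data reject. For 50/57 this is about 0.76 (exact). The interval is already planned, so this adds one sentence.

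A rule requiring the two 95% intervals not to overlap is not recommended. Against a 66/100 cohort it would need 50/57, with about 62% power at 0.88.

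**Cost.** SAP wording and one analysis of existing data, with no extra patients. The bar rises somewhat: about 47/57 against a 66/100 cohort, instead of 45/57 against a fixed 0.66. The stated power must be recalculated for the real control size (about 89% with 100 controls, if the rates are 0.66 and 0.88). If the cohort's own rate is above 0.66, the bar rises further.
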